## 15. Control of systematic bias/errors

In determining subject eligibility for the trial, the Investigator or his/her designee's assessment of inclusion/exclusion parameters will be used.

An independent Clinical Events Committee (CEC) will review clinical events that occur during the trial. The CEC will be blinded to the trial center and subject identification to the extent possible. An independent Data Safety Monitoring Board (DSMB) will review adverse events that occur during the trial.

## 16. Eligibility of subjects, exclusions and missing data

All subjects who are enrolled will be eligible for evaluation, regardless if they receive the control or active arm drug treatments for the assigned durations or not. Sensitivity analyses to account for missing data will be performed and may include imputation of missing data if deemed appropriate. The distribution of prognostic factors between subjects with and without data will be examined. Statistical models that account for censored data will be employed in appropriate circumstances, e.g., for time-to-event outcomes. Outlier values will be evaluated for their validity. All data will be included unless judged to be invalid. The robustness of the primary endpoint conclusion will be assessed based on these analyses.

## 17. Analysis set

The primary endpoint will be analyzed on an intent-to-treat basis and on a per-protocol basis analysis will also be performed. For intent-to-treat analysis, all subjects who sign the IRB/ECapproved written Informed Consent form and are enrolled into the trial will be included in the analysis, regardless of whether they receive the control or active arm drug treatments for the assigned durations or not. For per-protocol analysis, only subjects who receive the control or active arm drug treatments for the assigned durations will be included in the analysis.

The primary analysis set for testing of the primary endpoint is the intent-to-treat analysis set. No formal interim analyses are planned for the purpose of stopping this trial early for efficacy.

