## Protocol Synopsis

## ASPiRE Antiplatelet Strategy for Peripheral Arterial Interventions for Revascularization of Lower Extremities

PI	Name: [name]
	[contact]
	Email: [contact]
TRIAL OBJECTIVE	
Primary Objective	To evaluate whether clopidogrel 75 mg daily on a background of aspirin 81 mg/d for U.S. sites (75-100 mg/d for international sites) for clinically indicated duration or an additional 12 months will lead to an increased rate of primary patency, limb salvage, non-fatal myocardial infarction (MI), ischemic stroke, and survival, in patients receiving endovascular treatment of PAD at end of study treatment
Control Arm	clopidogrel 75 mg daily on a background of aspirin 81 mg/d for U.S. sites (75-100 mg/d for international sites) for clinically indicated duration with a minimum of 30 days.
Test Arm (as applicable)	clopidogrel 75 mg daily on a background of aspirin 81 mg/d for U.S. sites (75-100 mg/d for international sites) for clinically indicated duration + 12 months
Endovascular	Iliac
interventions included	Femoropoliteal
	Below-the knee
TRIAL DESIGN	
Trial Design	Prospective, two-arm, multicenter randomized clinical trial.
PlannedNumber of Subjects	202 subjects will be enrolled in each arm (total subjects = 404)
Clinically indicated dual	Clinically indicated DAPT duration will be based on the longest pre-
antiplatelet therapy	discharge following an index peripheral intervention procedure,
(DAPT) duration	DAPT duration. This will be determined based on: peripheral
	intervention device IFUs, preceding coronary intervention, acute
	coronary syndrome or other guideline-based clinical or device

	specific DAPT durations.
PlannedNumber of Sites / Countries	Approximately 18 investigational centers in the U.S are expected to participate.
	No center will be allowed to enroll more than 40% of planned total enrollment.
Primary Endpoint	Primary Endpoint (subject-based): The first occurrence of index limb arterial occlusion, surgical intervention, endovascular intervention, amputation of the affected limb (vessel occlusion or failure), MI, ischemic stroke or death at 12 months from index procedure or end of study treatment, whichever is longer
Secondary Endpoints	Secondary Endpoints through end of study treatment:
	• The first occurrence of any individual component of the primary endpoint

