## 6. Trial endpoints

Clinical endpoints will be analyzed in all subjects who are enrolled, regardless of whether the trial treatment administered successfully completed for the desired duration. A subject will be considered enrolled in the trial when he/she is randomized to one of the treatment arms of the study. All endpoints are subject-based unless otherwise specified.

The primary endpoint is subject-based of the longer of a 12-month or end of study treatment endpoint of the first occurrence of index limb arterial occlusion, surgical intervention,

endovascular intervention, amputation of the affected limb (primary patency and limb salvage), MI, ischemic stroke or death (survival)

The secondary endpoints are subject-based on the longer of a 12-month or end of study treatment endpoints that include: (a) the first occurrence of any individual component of the primary endpoint, (b) the first occurrence of the following during follow-up: cardiovascular death, or MI, or ischemic stroke, or any amputation above the ankle and (c) severe bleeding defined according to the Global Utilization of Streptokinase and Tissue plasminogen activator for Occluded coronary arteries (GUSTO) classification

The tertiary endpoint is based on the longer of a12-month or end of study treatment moderate bleeding according to the GUSTO classification

Clinically indicated DAPT duration will be based on the longest pre-discharge following index peripheral intervention procedure DAPT duration. This will be determined based on: peripheral intervention device IFUs, preceding coronary intervention, acute coronary syndrome or other guideline-based clinical or device specific DAPT duration.

Study treatment will be discontinued at the first occurrence of a primary endpoint as defined in the table below. Patients, however, can resume taking aspirin, Clopidogrel, or both based on their provider's clinical decision.

Primary endpoint definition(s)	Secondary/Tertiary endpoint definition(s)
Occlusion of the target limb documented by any imaging procedure performed clinically	As described in section 6, except for:
any maging procedure performed ennearly	GUSTO bleeding criteria:
Any surgical or endovascular	1. Severe or Life-threatening: Intracerebral hemorrhage resulting in substantial
revascularization procedure on the index limb	hemodynamic compromise requiring treatment
Amputation above the ankle of the index	2. Moderate: Requiring blood transfusion but not resulting in hemodynamic

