## 9. Method of assigning subjects to treatment

Patients scheduled for a planned discharge will be randomized on a 1: 1 basis using a central computerized randomization portal available through RedCap® to either of the following treatment groups:

ASA (81 mg/d for U.S. sites; 75-100 mg for international sites) + clopidogrel:for clinically indicated duration with a minimum of 30 days (control arm)

ASA (81 mg/d for U.S. sites; 75-100 mg for international sites) + clopidogrel 75 mg: for clinically indicated duration + 12m (treatment arm)

An inclusion and exclusion checklist needs to be completed via computerized randomization portal available through  $RedCap^{(R)}$  prior to randomization of the subject.

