## **12. Trial procedures**

The schedule of observations and assessments to take place during the trial are listed in **Table 2.** 

Table 2: Trial Event Schedule

	enrollment	30day (±7days)	6m  (± 15 days)	12m and q6m till end of study treatment  (±15 days)
Informed consent	+			
Inclusion/Exclusion	+			
Physical Examination 	+	+	+	+
Rutherford Classification	+	+	+	+
ABI	+	+	+	+
TASC classification	+			
Serum creatinine	+	+	+	+
Hemoglobin	+	+	+	+
Platelet count	+	+	+	+
Recommended Anti- Coagulant Therapy Assessment	+	+	+	+
WIQ (section 1)	+	+	+	+
AE assessment 		+	+	+
Concomitant medications	+	+	+	+

1. Physical examination includes gross assessment of standard organ systems (e.g., cardiac, pulmonary, etc).

2. AE assessments and reporting include AE, SAE and MAE.

- 3. End of study treatment visit will be performed when patient completes duration of assigned study treatment. This visit may fall between q6m visit schedule for some patients.
- 4. Phone visits can be done if patients refuse in-clinic visit during the follow up period, or who are do not show up to their follow up visits. Labs and ABIs will be collected and

documented, if available in their medical records during the follow up period. Study team should document 2 attempts to schedule in-clnic visits before phone visits are completed during follow-up

5. Patients who do not complete their follow up visits in -clinic will not be provided a refill of aspirin and Plavix (if randomized to the long arm) They will remain on the study as ITT and phone follow-up may be completed to collect data. Prescriptions may be renewed when patients complete an in-clinic visit.

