## **Primary Endpoint**

For the primary endpoint of 12-month composite of primary patency, limb salvage, MI, ischemic stroke and survival, with 95% confidence bounds will be calculated in the active arm and compared to control treatment duration. If this bound is less than that of control, then the primary endpoint will be considered met. All enrolled subjects are to be assessed for adverse events at follow-up visits. Assuming a maximum of 10% attrition due to non-compliance, loss to follow-up or death or non-compliance with follow-up, a minimum of 184 subjects in each arm are expected to be evaluable for the primary endpoint.

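### Read literally, the per-protocol set removes every extended-treatment subject with a primary event but keeps control subjects whose event follows the end of their shorter treatment

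*Combined protocol and SAP*

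**What the plan says.** Section 17 makes intention-to-treat the primary set and adds a per-protocol analysis of the primary endpoint. The membership rule is: "For per-protocol analysis, only subjects who receive the control or active arm drug treatments for the assigned durations will be included in the analysis". Section 19 repeats the per-protocol plan. The synopsis instead names an as-treated analysis.

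Four other provisions decide who meets that rule:

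- **Treatment stop (Section 6).** "Study treatment will be discontinued at the first occurrence of a primary endpoint as defined in the table below". It continues: "Patients, however, can resume taking aspirin, Clopidogrel, or both based on their provider's clinical decision".
- **Assigned duration (Section 9).** Control is assigned the clinically indicated duration, with a minimum of 30 days. The other arm is assigned treatment "for clinically indicated duration + 12m (treatment arm").
- **Endpoint window.** The synopsis assesses the composite "at 12 months from index procedure or end of study treatment, whichever is longer", and Section 6 agrees. Section 20 describes a fixed window: "For the primary endpoint of 12-month composite of primary patency, limb salvage, MI, ischemic stroke and survival".
- **Supply (Section 12, Table 2, footnote 5).** Subjects who do not attend clinic visits "will not be provided a refill of aspirin and Plavix (if randomized to the long arm").

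Nothing says that a stop required by Section 6 counts as completing assigned treatment.

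**The concern.** A per-protocol set should be defined by adherence. Here a primary event itself ends treatment, so membership depends on the outcome. It also depends on it differently by arm, because the assigned durations differ by 12 months while the windows largely overlap. The extended arm is reduced to subjects who had no event; the control arm keeps part of its events.

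The result would be reported beside intention-to-treat as a check on it. It could appear to confirm a benefit, or contradict a null or harmful result, for reasons unrelated to the drug. That matters in a trial that asks whether treatment should be extended.

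**Working it through.** **Inputs.** From the documents: 49% control event rate at 12 months and 202 per arm (Section 14), and the rules above. Assumed: no drug effect, constant hazard, one common D for all subjects, no other non-adherence. The documents give no distribution of D, so a range is shown.

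**The plan's own figure.** For 49% vs 34%, 80% power and two-sided 0.05, the continuity-corrected two-proportion formula gives 182 per arm, or 364; 364/0.9 is about 405. The plan states 368 and 404, so its sample size is reproduced closely. It gives no figure for the per-protocol set.

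**Who is kept**

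| First event | Control (assigned D) | Extended arm (assigned D + 12) |
|---|---|---|
| Before D | excluded | excluded |
| D to month 12 (D < 12) | kept, event counted | excluded |
| Month 12 to D + 12 | kept; after the control window if D < 12 | excluded |
| None by end of window and assigned treatment | kept | kept |

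With Section 20's 12-month window the extended-arm result is the same, because month 12 comes before D + 12.

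**Size with no drug effect.** Hazard λ = −ln(0.51)/12 = 0.0561 per month, and S(t) = exp(−λt).

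- Control kept = 202·S(D).
- Control rate = 1 − 0.51/S(D) = 1 − exp(−λ(12 − D)).
- Extended arm kept = 202·S(D + 12), with 0 events.

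Example at D = 6: S(6) = 0.714, control kept = 144, rate = 1 − 0.51/0.714 = 28.6%. Extended arm kept = 202 × 0.51 × 0.714 = 74.

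The last two columns give the share of simulated trials (10,000 each) in which an uncorrected chi-square test significantly favours the extended arm. HR 1.5 means that the extended arm is truly worse.

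| D (months) | Kept, control vs extended | Rate, control vs extended | No effect | HR 1.5 |
|---|---|---|---|---|
| 1 | 191 vs 97 | 46.1% vs 0% | 100% | 100% |
| 3 | 171 vs 87 | 39.6% vs 0% | 100% | 100% |
| 6 | 144 vs 74 | 28.6% vs 0% | 100% | 100% |
| 9 | 122 vs 62 | 15.5% vs 0% | 99.9% | 92% |
| 10 | 115 vs 59 | 10.6% vs 0% | 93% | 41% |
| 11 | 109 vs 56 | 5.5% vs 0% | 29% | 1% |
| 12 | 103 vs 53 | 0% vs 0% | 0% | 0% |

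**Hazard shape.** With Weibull shape 0.5 or 2, the no-effect figure is about 95% or more up to D = 9, then 66–70% at D = 10 and 1–13% at D = 11.

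**Mixed D (assumed shares)**

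- Equal shares of D = 1, 3, 6 and 12: 32.3% vs 0%; false benefit in 100% of trials.
- 10% D = 1, 20% D = 6, 70% D = 12: 14.2% vs 0%; 99.6%.
- 10% D = 1, 90% D = 12: 7.9% vs 0%; 68%.

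**If resumed drug counted as assigned treatment.** Suppose half the subjects with a treatment-stopping event were kept on this ground (assumed). Over 12 months with no drug effect, control vs extended is 47.6% vs 33.1%, 44.7% vs 34.2%, 40.5% vs 35.9% and 36.4% vs 37.5% at D = 1, 3, 6 and 9. With the longer-of window the extended arm becomes 34.9%, 39.8%, 46.6% and 52.9%. Size and direction then depend on resumption and on the window. Deaths would still be excluded.

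**Attrition figures (minor).** 404 × 0.9 = 363.6, against the minimum of 368 in Section 7; 36/404 = 8.9%. Power for 49% vs 34% is 83.4% at 184 per arm and 82.8% at 181 without continuity correction (79.9% at 181 with it).

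**The case against.** **The literal reading is uncharitable.** Section 6 orders the stop, so a subject stopped that way has followed the protocol and would naturally be kept. Section 6 also says that endpoints are analyzed in all enrolled subjects whether or not treatment was completed, and an arm with no events would be noticed. This makes deliberate exclusion unlikely. But the Section 6 sentence is general, whereas Section 17 is the only per-protocol definition and is explicit. A programmer applying it to exposure dates would build this set, and repairing the rule after seeing the data is what pre-specification should avoid.

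**No decision rests on this analysis.** That stands: no success rule or test hierarchy uses it. It limits the weight of the point without removing it.

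**One clarifying sentence would suffice.** With no other non-adherence it does. Otherwise, keeping subjects who adhere until an event or the end of assigned treatment, and comparing crude proportions, retains too many extended-arm events, because an early event shortens the long period over which adherence is required. At D = 3 with no drug effect, assumed annual non-adherence of 10%, 20% and 30% gives 49.1% vs 51.1%, 49.2% vs 53.5% and 49.3% vs 56.2%, with about 7%, 12% and 24% of trials significant. The residual bias is small at 10%, the only attrition rate in the documents, but footnote 5 makes long-arm non-adherence foreseeable.

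**Data for the fuller fix are coarse.** This stands in part. Medication is reviewed at 30 days and then at six-monthly visits, and at phone visits laboratory values and ABI are recorded only where available. Enrollment values remain usable.

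**Conclusion.** The concern holds. Applied as written, the per-protocol rule gives a 0% event rate in the extended arm whatever the drug does, while control keeps its events between D and month 12. This part follows from the text and needs no modelling.

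The size rests on a constant hazard at 49%, one common D and no other non-adherence. On those terms false benefit is near certain for D of 1 to 9 months, falls at 10 and 11, and is absent at 12. It persists with a harmful extended arm for D up to about 9 months, though at D = 9 it is sensitive to hazard shape (HR 1.5: 71% for Weibull shape 0.5, 24% for shape 2). How much of the trial is exposed depends on the share of subjects with D under 12 months, which the documents do not give.

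The change should be made, but it concerns a supportive analysis only. The intention-to-treat analysis and sample size are unaffected.

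**What to change.** **Section 17**

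- State that stopping study treatment because of a primary event is not a deviation and that the event is counted.
- Replace selection on completed duration: keep all randomized subjects, censor each at the first deviation from assigned treatment that is not an endpoint event, and compare arms by a time-to-event method over a common window, for example 12 months from the index procedure. Section 16 already foresees models for censored data.
- Define a deviation for both arms, including a control subject who continues clopidogrel after D.
- State that the censoring may be informative, and add a weighted sensitivity analysis using Table 2 covariates (Rutherford class, ABI, creatinine, hemoglobin), with enrollment values where later ones are missing.

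**Check of the fix.** With non-adherence of 0 to 30% a year unrelated to outcome, no drug effect and D = 1, 3, 6 or 9, the log-rank test rejected in 4.6% to 5.6% of trials (4,000 each), with Kaplan-Meier 49% vs 49%. In an assumed informative case (half the subjects with three times the event hazard and three times the stopping rate), the unweighted estimates were 48.6% vs 46.9% at D = 1, and weighting on that factor restored 49% vs 49%.

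**Limits to state.** A 12-month window differs from the longer-of endpoint. Assigned treatment differs in only (12 − D)/12 of it: 92%, 75%, 50%, 25% and 0% at D = 1, 3, 6, 9 and 12. Report how many subjects have D of 12 months or more.

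**Matching edits.** Name the same supportive analysis in the synopsis and Sections 17 and 19. In Sections 7 and 20, restate the evaluable number as about 363 (181 to 182 per arm), and remove death from the attrition wording because it is a primary event.

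**Cost.** A few lines of text, a recorded date of first treatment deviation and modest extra analysis. Randomization, sample size, treatment rules and the intention-to-treat analysis do not change.

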## 18. Availability of aspirin and clopidogrel

As both these drugs are approved worldwide and used routinely in post endovascular interventions, they would be used on the basis of use as per routine clinical practice and as per local/regional drug procurement and dispensing practices.

## **19. Statistical analysis**

Continuous variables will be summarized as mean±standard deviation and compared using the t-test or the Wilcoxon rank-sum test, as appropriate. Discrete variables will be presented as frequencies and group percentages and compared using the chi-square test. For all comparisons a two-sided probability of <0.05 will be considered statistically significant. All analyses were performed using the SAS 9.4 or recent version (SAS Institute Inc., Cary, North Carolina). Primary endpoint will be assessed as per an intention-to treat principle.

Subsequent analysis will also be performed based on per-protocol basis. Pre-specified

subgroup analyses will include:

- 1. Stent vs. non-stent groups
- 2. DES vs. BMS
- 3. Above and below-the knee intervention

4. Claudication vs. CLI groups

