Peripheral catheter interventions are performed under local anesthesia allowing early and full mobilization. However, as a result of this intervention, atherosclerotic plaques are ruptured and platelets aggregate at the site of injury. Extensive vessel wall damage coupled with low shear stress and poor infrapopliteal outflow are mostly responsible for the occurrence of reocclusion.

Additionally, in the initial phase after catheter intervention, a hypercoagulable state prevails, as parameters of activated coagulation, including thrombin-antithrombin complexes (TAT), D-Dimer and Fibrinopeptide A (Fa) become elevated in the plasma. This activated coagulation system produces conditions favorable for early thrombotic occlusion, where 'early' is usually defined as a period covering the first four weeks after the intervention. Subsequently, intimal hyperplasia may follow which is responsible for intermediate and late-term restenosis and reocclusion. Intimal hyperplasia occurs as a result of denudation (tearing off of the inner lining) of the endothelium caused by manipulation of the vessel wall with the catheter. Reported rates of arterial reocclusion or symptomatic restenosis following femoropopliteal PTA are between five and twenty-five per cent for early events and about 40% one year. The five year patency rate was reported to be 83% for iliac and 58% for femoropopliteal PTA, whilst patients with stenoses or occlusions of less than 3 cm had a favorable long-term patency rate of 74%

Patients with CLI or those subjected to local thrombolysis show higher incidences of reocclusion. The implantation of drug-eluting or nitinol stents, or treatment by intravascular brachytherapy following PTA are considered as interventions with the capacity of reducing the occurrence of intimal hyperplasia, however may be associated with delayed endothelialization

and increased risk of thrombosis.

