## 14. Sample size estimate

The occurrence of the primary endpoint is expected to be approximately 49% in the control group, derived on the basis of current literature review and preliminary data form XLPAD registry.

A 30% relative risk reduction in the incidence of primary endpoint would be clinically important. To detect a 30% relative reduction in the primary event rate from 49% to34%  with 80% power at the two-sided, 0.05 significance level, assuming a 12-month recruitment period and a 10% dropout rate at 1 year, a total of 404 patients will be randomized (202in each group) and followed-up for endpoints for longer of a 12-month or end of study treatment period.

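### No covariate-adjusted or stratified analysis is specified for the primary endpoint, although the protocol itself links CLI and arterial level to outcome

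*Combined protocol and SAP*

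**What the plan says.** **Analysis.** Section 19 states that "Discrete variables will be presented as frequencies and group percentages and compared using the chi-square test". The sentence covers discrete variables in general and does not mention the primary endpoint. The Primary Endpoint text in Section 20 sets a different criterion: 95% confidence bounds are calculated in the active arm, and the endpoint is met if the bound is below that of control. It names no test, model or covariate. Section 16 allows models for censored data where appropriate and Section 20 adds Kaplan-Meier plots, but neither is assigned to the primary comparison.

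**Allocation.** Section 9 has patients "randomized on a 1: 1 basis using a central computerized randomization portal". Neither that section nor the synopsis names a stratification factor.

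**Prognosis.** Section 3 states that "Patients with CLI or those subjected to local thrombolysis show higher incidences of reocclusion" and reports five-year patency after angioplasty of 83% for iliac and 58% for femoropopliteal treatment. Section 2 contrasts good iliac patency with poor infra-inguinal patency.

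**Data.** Table 2 records Rutherford class at enrolment. Section 19 lists claudication vs CLI and above/below knee among the pre-specified subgroups.

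**The concern.** The eligibility criteria admit Rutherford 2, 3 and 4 or above, and treatment from the iliac to the tibial arteries. Occlusion and repeat revascularisation of the index limb are components of the primary endpoint, so factors that the protocol associates with reocclusion and patency are likely to predict it. The plan uses them only to define subgroups. Neither the design nor the primary analysis is stated to take account of them.

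Two things are at stake: some precision, and the ability to deal with a chance imbalance by a rule fixed in advance. If the arms differ visibly in CLI share and no adjustment was pre-specified, any adjusted result will look like a choice made after the data were seen.

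**Working it through.** **1. The plan's own sample size.** Section 14 expects "The occurrence of the primary endpoint is expected to be approximately 49% in the control group" and sizes the trial "To detect a 30% relative reduction in the primary event rate from 49% to34"%, "with 80% power at the two-sided, 0.05 significance level", "assuming a 12-month recruitment period and a 10% dropout rate at 1 year".

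- Two proportions, pooled variance under the null: n = [1.96·√(2·0.415·0.585) + 0.8416·√(0.49·0.51 + 0.34·0.66)]² / 0.15² = (1.366 + 0.580)² / 0.0225 ≈ 168.2, so 169 per arm.
- With continuity correction: (168.2/4)·[1 + √(1 + 4/(168.2·0.15))]² ≈ 181.3, so 182 per arm, 364 in total (stated: 368).
- With 10% dropout: 364/0.9 = 404.4 (stated: "a total of 404 patients will be randomized").

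The stated size therefore behaves like an unadjusted two-proportion test. At 184 evaluable per arm, power without continuity correction is Φ[(0.15·√184 − 1.366)/0.689] = Φ(0.971) ≈ 83.4%.

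**2. Assumptions for the adjusted analysis.** The documents give neither prevalences nor odds ratios. Assumed: CLI in 40%, below-knee treatment in 30%, the two independent, overall rates 49% and 34%, and odds ratios from 1.5 to 4. The four strata (neither, CLI only, below-knee only, both) then have weights 0.42, 0.28, 0.18 and 0.12.

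**3. Variance, shown for odds ratios 2 and 2.** Control rates by stratum are 0.37, 0.54, 0.54, 0.70; test rates are 0.24, 0.38, 0.38, 0.55.

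- Unadjusted: 0.49·0.51 + 0.34·0.66 = 0.4743.
- Within strata, Σw·p(1−p): control 0.2374, test 0.2147. Spread of the stratum differences around 0.15: 0.0002. Sum 0.4523.
- Ratio 0.4743/0.4523 = 1.049 (1.051 with unrounded rates). This is like a sample about 5% larger.

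**4. Range.** Power is simulated with 184 per arm and 20,000 trials per row. The test is Pearson chi-square or a Cochran-Mantel-Haenszel (CMH) test over the four strata. The last column is 169 divided by the variance ratio.

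| Odds ratios (CLI, below knee) | Variance ratio | Pearson power | CMH power | Per-arm n for 80% power |
|---|---|---|---|---|
| 1, 1 | 1.000 | 83.9% | 83.6% | 169 |
| 1.5, 1.5 | 1.018 | 83.1% | 83.4% | 166.1 |
| 2, 2 | 1.051 | 83.7% | 85.1% | 160.7 |
| 3, 2 | 1.093 | 83.7% | 86.4% | 154.7 |
| 3, 3 | 1.126 | 84.0% | 87.8% | 150.1 |
| 4, 3 | 1.164 | 83.6% | 88.3% | 145.2 |

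Across the rows with a prognostic effect the gain is 0.3 to 4.7 points of power, or about 3 to 24 patients per arm. With no prognostic effect (first row) stratification costs about 0.3 points. With 49% in both arms, simulated type I error is 5.0–5.5% for Pearson and 4.7–5.2% for CMH.

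**5. Chance imbalance, if randomisation is simple.** With 202 per arm and 40% CLI, the standard deviation of the between-arm difference in CLI share is √(2·0.4·0.6/202) = 0.0487.

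- P(difference above 5 points) = P(|Z| > 1.026) = 0.305. It is 0.21 at 20% prevalence and 0.315 at 50%.
- P(difference above 10 points) = 0.04 at 40% prevalence.

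To gauge the consequence, assume control rates of 40% in claudication and 62.5% in CLI, which average to 0.6·40 + 0.4·62.5 = 49%. A 5-point imbalance then moves the crude difference by 0.05·22.5 = 1.1 points. The standard error of that difference is √(0.4743/184) = 5.1 points, so the shift is about 0.2 standard errors.

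**The case against.** The strongest reply is that an unadjusted comparison of randomised arms is legitimate. Chance imbalance is already allowed for in the type I error, which the simulation puts near 5%, and the trial has about 83% power without adjustment. That stands, and it limits the point to efficiency.

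A reader might infer more than the documents support:

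- *That the primary test is a chi-square.* Section 19 does not say so, and Section 20 gives another rule. What can be said is that the comparison is unadjusted on either reading.
- *That randomisation is unstratified.* The documents only describe no strata. If the portal does stratify, the imbalance figures fall, and the analysis should then reflect the strata used.
- *That the factors are strong predictors.* For CLI no figure is given. For level, the figures are five-year iliac and femoropopliteal patency; none concerns below-knee treatment or this composite, which also counts MI, stroke and death.
- *That clinically indicated duration is a further strong prognostic factor.* No section calls it prognostic and it is not an item in Table 2. Follow-up runs to the longer of 12 months or end of treatment. With a 6-month indicated duration, for example, that is 12 months in control and 18 in the test arm. Adjusting for duration leaves this difference between arms in place.

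A practical objection also stands. Table 1 allows treatment at one or more locations, so iliac, femoropopliteal and below-knee are not exclusive categories. A yes/no factor for any below-knee treatment avoids this and stays close to the plan's own subgroup, although it is not the contrast for which Section 3 gives patency figures.

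**Conclusion.** The point holds as a modest, optional improvement. The plan specifies no adjusted or stratified primary analysis and describes no stratified randomisation, while identifying two outcome-related factors that it already needs for its subgroups. Under the stated assumptions the gain is about 0 to 5 points of power, and the unadjusted variance is about 2% to 16% larger than the adjusted one. The true gain depends on prevalences and odds ratios that the documents do not give.

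The documents do not support reading the omission as a bias or a loss of type I error control: a two-sample chi-square without covariates remains valid. That statement does not extend to the confidence-bound rule in Section 20, which is not clearly a two-sample test. Its disagreement with Section 19 needs settling in any case, and adjustment can be decided in the same edit.

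**What to change.** In Section 19, and in the Primary Endpoint text of Section 20 so that the two agree:

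1. Name one primary between-arm comparison, adjusted for claudication vs CLI and for any below-the-knee treatment (yes/no). The second factor also classifies multilevel patients. Use Mantel-Haenszel over the four strata, or a regression model with a standardised risk difference.
2. State how CLI is derived from Rutherford class and that both factors take values fixed before randomisation.
3. Keep the unadjusted comparison as supportive.
4. State in Section 9 whether the portal stratifies, and on what.

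Do not add indicated duration as a prognostic covariate in the hope of resolving unequal follow-up; that needs its own solution.

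The cost is wording only. Randomisation, sample size and data collection are unchanged. The text should be fixed before outcome data by arm are seen.
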